5.3.2.2. Discontinuation-Emergent Signs and Symptoms (DESS) Scale

The DESS Scale is a clinician-rated instrument of 43 items used to evaluate signs and symptoms associated with discontinuation or interruption of monoamine reuptake inhibitor treatment. Each of the 43 signs and symptoms is assessed and placed in one of the following categories: new symptom, old symptom but worse, old symptom but improved, old symptom but unchanged, and symptom not present. Each sign and symptom that is placed in the category new symptom or in the category old symptom but worse receives 1 point. All other categories receive 0 points. The total DESS score is the sum of the number of points, which corresponds to the number of

symptoms rated as either a new symptom or as an old symptom but worse. The score ranges from 0 to 43, where higher scores indicate more discontinuation-emergent signs and symptoms.

The DESS is collected at Week 52/EOT, and Weeks 53, 54 and 55/EOS for subjects who enter the withdrawal period.

5.3.2.3. Montgomery-Asberg Depression Rating Scale (MADRS)

The MADRS is a clinician-rated assessment of the subject's level of depression. This scale contains 10 items that measure apparent and reported sadness, inner tension, reduced sleep and appetite, difficulty concentrating, lassitude, inability to feel, and pessimistic and suicidal thoughts. Each item is scored in a range of 0 to 6, with higher scores indicating increased depressive symptoms. The score for each question will be summed to compute a total score ranging from 0 to 60. If the response to any question is missing, the total score will be missing.

The MADRS is collected at Weeks 24, 52/EOT, and Weeks 53, 54 and 55/EOS for subjects who enter the withdrawal period.

5.3.2.4. Hamilton Anxiety Rating Scale (HAM-A)

The HAM-A is a rating scale developed to quantify the severity of anxiety symptomatology. It consists of 14 items, each defined by a series of symptoms. The 14 items are: anxious mood, tension, fears, insomnia, intellectual, depressed mood, somatic (muscular), somatic (sensory), cardiovascular symptoms, respiratory symptoms, gastrointestinal symptoms, genitourinary symptoms, autonomic symptoms, and behavior at interview. Each item is rated on a 5-point scale, ranging from 0 (not present) to 4 (severe/disabling). The score for each question are summed to compute a total score ranging from 0 to 56. If the response to any question is missing, the total score is missing. A higher score is associated with a greater degree of anxiety. A score of ≥ 14 has been suggested to indicate clinically significant anxiety.

The HAM-A is collected at Weeks 24, 52/EOT, and Weeks 53, 54 and 55/EOS for subjects who enter the withdrawal period.

6. Statistical Methods

6.1. General Analysis Definition

6.1.1. Analysis Period and Study Day

Two scopes of data for a subject are considered in this study. Each scope of data consists of a specific portion (subset) of study data for the subject.

6.1.1.1. Open-Label Treatment Period (On Treatment)

The day of the 1st dose date in the extension study will be denoted as study Day 1. All measurements at each visit will be assigned a study day relative to this date. All data collected on/after Day 1 for subjects previously randomized to placebo group in core study or on/after the extension baseline visit for subjects previously randomized to dasotraline groups and up to Week 52, including the End-of-treatment/Early Withdrawal visit, will be considered within the open-label treatment phase. That is to say, the start of the open-label treatment period is defined as Day 1 for subjects previously randomized to placebo group and the OL Baseline visit date for subjects previously randomized to dasotraline groups; the end of the open-label treatment phase is defined as the maximum of the last date of administration of study medication and the withdrawal/ completion date.

The start and end of open-label treatment period are given below:

- **Start of treatment period** =
 - = Date of the first study medication administration for subjects previously randomized to placebo group
 - = Date of the OL Baseline visit for subjects previously randomized to dasotraline;
- **End of treatment period** = maximum of the last date of administration of study medication and the withdrawal/ completion date (ie, Week 52/EOT visit date).

Each subject's assessment at each visit in pre-treatment and treatment period will be assigned a study day with respect to the first dose date in the extension study.

- Study Day = Assessment date – the first dose date in the extension study + 1; if assessment date \geq the first dose date in the extension study
- Study Day = Assessment date – the first dose date in the extension study; if assessment date < the first dose date in the extension study

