6.1.1.3. Overall Study Period

Overall study period is defined as a combination of the open-label treatment period and withdrawal period. See [Table 3](#) below for summary of definition of all analysis periods and study day used for this study.

Table 3: Definition of Analysis Study Period

Analysis Study Period	Start Date	End Date	Applicable Scope
Open Label Treatment Period	Day 1*	EOT ^a	Subjects previously randomized to Placebo group
	Baseline Visit Date	EOT ^a	Subjects previously randomized to Dasotraline
Withdrawal Period	Day 0**	EOS ^b	Withdrawal Population
Overall Study Period	Day 1*	EOS ^b	Subjects previously randomized to Placebo group
	Baseline Visit Date	EOS ^b	Subjects previously randomized to Dasotraline group
Note: *: the day of the first dose of open-label study medication. ^a : Week 52 visit/ early withdrawal visit **: the day of the last dose of open-label study medication. ^b : last scheduled or unscheduled (site/phone contact) visit in withdrawal period			

Except for adverse event data, summaries and analyses of all data on OL treatment are based on the portion of study data that fall in the open-label treatment period. For adverse events, see [Section 7.4.2](#) for how a study subject is considered to be on treatment during the treatment period (ie, last study medication administration + 7 days for AE or +14 days for Serious AE).

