6.1.5. Aggregated Analysis Timepoint

An aggregated analysis timepoint named as ‘any OL treatment period (treatment emergent)’ will be derived for selected safety assessments (eg, the worst case analysis) as below.

- Any OL treatment period (treatment emergent): defined as any assessment collected in open-label treatment period (see [Section 6.1.1.1](#)).

Specifically, the aggregated analysis timepoint of any OL treatment period (treatment emergent) will be applied on the following worst-case analysis:

- Markedly Abnormal Laboratory Values (MALV) ([Section 7.4.3.1](#), [Table 6](#))
- Markedly Abnormal Vital Signs (MAVS) ([Section 7.4.5.1](#), [Table 9.1](#))
- QTc prolongation ([Section 7.4.4.1](#), [Table 7](#))
- ECG abnormality ([Section 7.4.4.1](#), [Table 8](#)).
- C-SSRS ([Section 7.4.7](#))

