7.4.3.1. Treatment Period

Descriptive statistics (N, mean, standard deviation, median, and range) will be reported for each continuous laboratory analyte at DB baseline, OL baseline, each post-OL baseline time point, and endpoint for observed actual value as well as change from DB baseline and OL baseline, respectively. Categorical results (eg, urinalysis tests) will be summarized at DB baseline, OL baseline, each post-OL baseline visit, and endpoint by analysis group using frequency and percentage. All lab values will be presented in the data listings.

Results for glucose and lipid tests (HDL cholesterol, LDL cholesterol, total cholesterol, and triglycerides) will be presented separately by fasting status, which includes fasting only and overall (fasting, non-fasting, or unknown).

The normal reference ranges for laboratory tests will be used to determine whether the laboratory test value is below, within, or above the normal range. Shifts from DB baseline and shift from

322

OL baseline over time will be produced by analysis group to show the percentage of subjects with laboratory test values below, within, and above the normal range. Criteria for Markedly Abnormal Laboratory Values (MALV) per International System of Units (SI) unit of selected laboratory parameters can be found in [Table 6](#). Equivalent MALV criteria for conventional unit are provided in [Attachment 9.4.2](#). The criterion of MALV is satisfied if a value falls into the markedly abnormal range at an assessed visit or if subjects have experienced at least once MALV in the open-label treatment period. The number and percentage of subjects with a particular MALV at each OL visit, endpoint, and during the open-label treatment period (treatment emergent, up to and including endpoint), will be presented by analysis group.

Table 6: – Criteria for Markedly Abnormal Laboratory Values (MALV) (SI Unit)

Laboratory Test	Criteria for Markedly Abnormal Status	
	Low	High
Hematology		
Hematocrit	Male: ≤ 0.37 Female: ≤ 0.32	Male: ≥ 0.60 Female: ≥ 0.54
Hemoglobin	Male: ≤ 115 g/L Female: ≤ 95 g/L	Male: ≥ 190 g/L Female: ≥ 175 g/L
RBC	$\leq 3.5 \times 10^{12}$ /L	$\geq 6.4 \times 10^{12}$ /L
Total WBC Count	$\leq 2.8 \times 10^9$ /L	$\geq 16 \times 10^9$ /L
Basophils	N/A	$\geq 10\%$ $\geq 1.6 \times 10^9$ /L
Eosinophils	N/A	$\geq 10\%$ $\geq 1.6 \times 10^9$ /L
Lymphocytes	N/A	$\geq 75\%$ $\geq 12.0 \times 10^9$ /L
Monocytes	N/A	$\geq 15\%$ $\geq 2.4 \times 10^9$ /L

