7.4.4.1. Treatment Period

Descriptive statistics (eg, mean, SD, median, range, 95% CI) for observed actual value at the DB baseline, OL baseline, each post-OL baseline visit, and endpoint and changes from DB baseline and OL baseline, respectively will be displayed for continuous variables (ie, HR, QRS, QTcF, etc) by analysis group.

The overall ECG assessment is conducted by central reading and a determination is made whether the reading is normal (or absent if applicable) or abnormal). Shifts from OL baseline and Shifts from DB baseline over time will be produced by analysis group.

Bazett and Fridericia corrected QT_c values will be classified as having QT_c prolongation according to [Table 7](#).

Table 7: – QTc Prolongation

QTc Prolongation
> 450 msec for males
> 470 msec for females
> 480 msec
> 500 msec
Increase from OL baseline QTc ≥ 30 msec
Increase from DB baseline QTc ≥ 30 msec
Increase from OL baseline QTc ≥ 60 msec
Increase from DB baseline QTc ≥ 60 msec

The number and percentage of subjects having a QT_c prolongation using Fridericia correction method for DB baseline, OL baseline, post-OL baseline visit, endpoint, and any open-label treatment period (treatment emergent, the worst case), will be summarized by analysis group. A listing of ECG data for subjects with at least one prolonged QT_c will also be produced.

For other ECG parameters, subjects are classified as normal or abnormal using the limits specified in [Table 8](#). For abnormal ECG parameter reporting, counts and percentages of subjects will be presented for DB baseline, OL baseline, each post-OL baseline visit, endpoint, and any open-label treatment period (treatment emergent) by analysis group.

Table 8: – Definition of Abnormal ECG Values by Parameter

ECG parameter (unit)	Abnormally Low	Abnormally High
HR (bpm)	≤50	≥100
PR interval (msec)	N/A	≥210
QRS interval (msec)	N/A	≥120
QT interval (msec)	N/A	> 500

Note: N/A = Not Applicable

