7.4.5. Vital Signs, Weight, and BMI

7.4.5.1. Treatment Period

Descriptive statistics (mean, SD etc.) will be provided for observed at the DB baseline, OL baseline, post-OL baseline visit, and endpoint, and change from DB baseline and OL baseline values, respectively of each vital sign parameters, weight, and BMI listed below:

- Systolic blood pressure (SBP) in supine and standing positions
- Diastolic blood pressure (DBP) in supine and standing positions
- pulse rate in supine and standing positions
- Orthostatic change in SBP
- Orthostatic change in DBP
- Orthostatic change in pulse rate
- Respiratory rate
- Temperature
- Body weight and BMI,

Percent change from DB baseline and OL baseline values in weight and BMI will be summarized in a similar way.

The number and percentage of subjects with Markedly Abnormal Vital Signs (MAVS), defined in [Table 9.1](#), will be presented by analysis group at DB baseline and OL baseline, post-OL baseline visits, endpoint, and any open-label treatment period (treatment-emergent, the worst case).

A listing of subject data for those who satisfy MAVS during the open-label treatment period will be presented.

Table 9.1: – Criteria for Markedly Abnormal Vital Signs and Weight

Parameter (unit)	Markedly Low	Markedly High
SBP (supine, standing) (mmHg)	<90	≥180
	Value ≤ 90 and ≥ 20 decrease from baseline	Value ≥ 180 and ≥ 20 increase from baseline
DBP (supine, standing) (mmHg)	<50	≥105
	Value ≤ 50 and ≥ 15 decrease from baseline	Value ≥ 105 and ≥ 15 increase from baseline
Pulse rate (supine, standing) (bpm)	<50	≥120
	Value ≤ 50 and ≥ 15 decrease from baseline	≥120 and increased >15 from baseline
Weight (kg)	≥ 7% decrease from baseline	≥ 7% increase from baseline
Temperature (°C)	N/A	Value ≥ 38.3°C and ≥0.8°C

		increase from baseline
Orthostatic Criteria		
SBP orthostatic criteria (mmHg)	≥ 20 mmHg reduction from supine to standing position	N/A
DBP orthostatic criteria (mmHg)	≥ 10 mmHg reduction from supine to standing position	N/A
Orthostatic tachycardia (bpm)	N/A	≥ 20 bpm increase from supine to standing position in pulse rate.

BMI measurements will be used to classify a subject’s weight status as underweight, normal, overweight or obese using [Table 9.2](#) and as underweight/normal, overweight, obesity class I, obesity class II, and obesity class III using [Table 9.3](#).

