7.4.7. Columbia Suicide Severity Rating Scale (C-SSRS)

According to FDA draft guidance for suicidal ideation and behavior ([2]), the following C-SSRS outcomes, which have binary responses (yes/no), will be re-ordered and numbered to facilitate the further definitions of the composite endpoint and comparative endpoint of C-SSRS as below.

Category 1 – Wish to be Dead

Category 2 – Non-specific Active Suicidal Thoughts

Category 3 – Active Suicidal Ideation with Any Methods (Not Plan) without Intent to Act

Category 4 – Active Suicidal Ideation with Some Intent to Act, without Specific Plan

Category 5 – Active Suicidal Ideation with Specific Plan and Intent

Category 6 – Preparatory Acts or Behavior

Category 7 – Aborted Attempt

Category 8 – Interrupted Attempt

Category 9 – Actual Attempt

Category 10 – Completed Suicide

Category 11 – Self-injurious behavior without suicidal intent

Unless otherwise specified, C-SSRS table outputs will be presented by analysis group for one analysis time point ‘Any extension (treatment emergent)’, whose definition is given in [Table 10](#).

The analysis time point is applied to suicidal ideation score and ideation intensity total score.

Table 10: Definition of Analysis Timepoint

Analysis Timepoint	eCRF Visit(s) to be Involved	C-SSRS Version /Assessment Period	Derivation Rule
Any extension visit (treatment emergent) ^(a)	all visits in the open-label treatment period (up to EOT)	Since last visit	Most severe value
Any withdrawal visit	all visits after the last study dose	Since last visit	Most severe value

^(a): including all visits in open-label treatment period (see [Section 6.1.1.1](#)).

At each analysis time point, the following binary variables will be derived.

- Any Suicidal Ideation (Categories 1-5)
- Any Suicidal Behavior (Categories 6-10)
- Any Suicidality (Categories 1-10)
- Individual Item for Category 6-11, respectively.

Comparative endpoints for ‘Emergence’ (outcomes that include events that first emerge) and ‘Worsen’ (outcomes that include events that worsen) will be derived as below. See [Table 11](#).

Table 11: Comparative Endpoint of C-SSRS Relative to DB Baseline

Comparative Endpoints	Analysis Time Points Involved	Derivation Rule
Emergence of Suicidal Ideation	DB Baseline ^(a) Any extension visit (treatment emergent) ^(b)	No suicidal ideation at DB Baseline, and any type of suicidal ideation in ‘any extension visit (treatment emergent)’

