7.4.8.2. Neurological Examination

Frequency distribution of each category of assessment (ie, Cranial Nerves, Motor System, sensory System, Reflexes, Coordination, Gait and Romberg's test) will be summarized by analysis group at each visit. A shift table of each assessment for DB and OL baseline to endpoint and the worst case during open-label treatment period will also be presented by analysis group.

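### The SAP's treatment-emergent worst-case time point takes in the OL Baseline value for prior-dasotraline subjects but not for prior-placebo subjects

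*SAP*

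**What the plan says.** SAP 6.1.1.1 and Table 3 give the open-label treatment period two starts. For subjects randomized to placebo in the core study it is the first open-label dose (Day 1). For subjects randomized to dasotraline it is the OL Baseline visit, and the rule is inclusive: data "on/after the extension baseline visit for subjects previously randomized to dasotraline groups and up to Week 52" belong to it.

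The text under Table 3 applies this period to everything except adverse events: "summaries and analyses of all data on OL treatment are based on the portion of study data that fall in the open-label treatment period".

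SAP 6.1.5 builds the worst-case time point on it: "Any OL treatment period (treatment emergent): defined as any assessment collected in open-label treatment period". That time point is listed for markedly abnormal laboratory values, markedly abnormal vital signs, QTc prolongation, ECG abnormality and C-SSRS. The analysis sections repeat it: laboratory values "during the open-label treatment period (treatment emergent, up to and including endpoint" (7.4.3.1), and QTc in "any open-label treatment period (treatment emergent, the worst case" (7.4.4.1). These phrases give an upper bound or none; neither gives a lower bound that would leave out the baseline visit.

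The OL Baseline visit is the core Week 12 visit, on the day before the first open-label dose (SAP Section 3; Protocol 11.5.1). SAP 6.1.3.2 carries its values over as the OL Baseline.

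**The concern.** A baseline value should not also count as an event that emerged after baseline. Under these rules it can in one analysis group and not in the other.

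Laboratory, ECG, vital-sign and weight changes belong to the primary safety objective. A Das-Das subject who crosses a limit only at core Week 12 would be reported as treatment emergent in the extension, although the finding arose in the core study. The Das-Das and Pbo-Das percentages would then answer different questions, and All-Das would mix the two. The distortion weighs most on rare limits and on subjects who stop early and have few later assessments.

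**Working it through.** **Step 1: apply the period rules to single assessments.** SAP 6.1.1.1 gives study day = assessment date − first dose date before the first dose, with 1 added from the first dose onward.

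| Assessment | Study day | In period, Pbo-Das | In period, Das-Das | OL Baseline by Table 4 window (<1) |
|---|---|---|---|---|
| OL Baseline visit | −1 | no | yes | yes |
| Week 2 | 14 | yes | yes | no |

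Only the Das-Das OL Baseline record holds both roles.

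**Step 2: look for an exclusion.** Where the SAP wants the baseline record out, it says so. Endpoint (6.1.4.1) and the C-SSRS ideation shift (7.4.7.1) are both limited to post-OL-baseline assessments. SAP 6.1.5 has no such limit. In the protocol's statistics section the split start appears only in the definition of treatment-emergent adverse events (15.3.3.1), where it suits event onset under uninterrupted dosing. The SAP extends it to measurements without giving a reason.

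**Step 3: sort the outputs.**

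- Exposed: markedly abnormal laboratory values; absolute QTc and other ECG limits; QTc increase from DB baseline; absolute and orthostatic vital-sign limits.
- Exposed only if the baseline is DB baseline: the change criteria in Table 9.1, such as "Value ≥ 180 and ≥ 20 increase from baseline", and the 7% weight criteria. The table does not name the baseline.
- Not exposed: changes from OL baseline (the baseline value differs from itself by zero), by-visit tables (Table 4 puts days below 1 under OL Baseline), Endpoint, and shift tables.

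**Step 4: count scheduled looks (Protocol Table 2).** Open-label looks are laboratory 4 (Weeks 12, 24, 36, 52), ECG 5 (Weeks 4, 12, 24, 36, 52) and vital signs 14 (Weeks 2, 4, then every 4 weeks to 52). Das-Das gains one: 5 vs 4, 6 vs 5 and 15 vs 14.

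**Step 5: illustrate the size.** The plan states no figure to reproduce, so every input here is an assumption.

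- Das-Das size: with equal allocation within each core study and equal completion, (300 × 1/2 + 480 × 2/3)/780 = 470/780 = 60%, or about 300 of 500.
- Risk per assessment p: 1% to 5%, the same at every look.
- Within-subject correlation r, beta-binomial: s = 1/r − 1, a = p·s, b = (1 − p)·s. P(no abnormal value in k looks) = product over i = 0 to k − 1 of (b + i)/(a + b + i). At r = 0 this is (1 − p)^k.
- Extra subjects = 300 × [P(any in k + 1) − P(any in k)].

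One laboratory limit, 5 vs 4 looks:

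| r | p = 1% | Extra | p = 5% | Extra |
|---|---|---|---|---|
| 0 | 4.90% vs 3.94% | 2.9 | 22.62% vs 18.55% | 12.2 |
| 0.25 | 3.24% vs 2.82% | 1.2 | 15.38% vs 13.52% | 5.6 |
| 0.5 | 2.26% vs 2.07% | 0.6 | 10.96% vs 10.06% | 2.7 |
| 0.75 | 1.56% vs 1.49% | 0.2 | 7.68% vs 7.32% | 1.1 |
| 1 | no difference | 0 | no difference | 0 |

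At r = 0.5, one ECG limit gives 0.5 to 2.2 extra subjects and one vital-sign limit 0.2 to 0.8. For a subject who stops early with a single end-of-treatment laboratory sample (2 vs 1 looks, r = 0.5), the risk of being counted rises from 1.00% to 1.50%, or from 5.00% to 7.38%.

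**The case against.** **Exclusion may be what the authors meant.** Protocol 15.3.2 defines OL Baseline as an assessment from the double-blind period, and SAP Section 4 declares no departure from the protocol. SAP Section 3 lists the baseline visit apart from the treatment period, and Protocol 11.5.2 starts that period at Visit 2E. SAP 6.1.3.2 keeps core end-of-treatment data out of the extension database, and 7.4.4.1 and 7.4.5.1 report OL baseline separately from the any-period result. This makes exclusion a plausible intent. It does not override a rule that includes the baseline visit by name and date. The storage text does not settle it, since the values must still be brought in as OL Baseline. Nor does separate reporting, since Endpoint is also reported separately and yet lies inside the aggregate.

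**Das-Das subjects were on drug at core Week 12.** Dosing does not stop between studies, so starting each group's period by exposure is a coherent idea. But it would equally admit the earlier core weeks on dasotraline, and the SAP admits only the final visit, which is also this study's reference value.

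**The size is assumed and leans high.** This stands. Exclusion 4 and Protocol 12.2 can keep out subjects with clinically significant OL Baseline abnormalities. They rest on investigator judgement and will not remove every flagged value, but they make the baseline risk lower than the constant risk in the model. Zero correlation is implausible for repeated laboratory values.

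**Two wider readings are tempting.** A reader might infer that the neurological worst-case shift is contaminated, because 7.4.8.2 plans "A shift table of each assessment for DB and OL baseline to endpoint and the worst case during open-label treatment period". SAP Section 7 defines shift tables as baseline against post-baseline, and 6.1.5 does not list that examination, so it is not affected. A reader might also infer inflated suicidality counts, because Table 10 uses "all visits in the open-label treatment period (up to EOT" and refers back to 6.1.1.1. That is doubtful: SAP 5.3.1 lists open-label C-SSRS collection from Week 2, the baseline C-SSRS is carried over from the core study, and Exclusion 3 bars ideation items 4 and 5 at OL Baseline.

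**Conclusion.** The rule is wrong as written, for a limited set of outputs. Taken together, SAP 6.1.1.1, Table 3 and 6.1.5 let a Das-Das core Week 12 value serve as both baseline and treatment-emergent finding, and do not do so for Pbo-Das.

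The likely effect is small: of the order of 0.2 to 2.7 subjects per limit at correlation 0.5, probably fewer after eligibility screening, and none if abnormal values fully persist. The actual number cannot be known from the documents.

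A reader might go further and infer that a comparison between the groups is biased. The documents do not support that, because no test or inferential comparison is planned. What suffers is the accuracy of a reported incidence and the meaning of the pooled All-Das column. Confidence is medium, because the intended programming may already leave the value out.

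**What to change.** Add one sentence to SAP 6.1.5: *This time point includes only assessments made after the OL Baseline assessment, in both analysis groups.* Repeat it in Table 10 for consistency. Keep the OL Baseline visit date as the Das-Das start for adverse events only, as 7.4.2 already states. Show OL Baseline values only in an OL Baseline row; 7.4.3.1 does not name one for markedly abnormal laboratory values, so add it there. No edit to 7.4.8.2 is needed.

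The cost is the sentence, that row and a date filter in programming, with no new data and no protocol change. On-drug core Week 12 values leave the worst-case row but stay visible at OL Baseline. If exclusion was always intended, the sentence simply records it.
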